2.4.2.2 Safety endpoints

All safety endpoints will be compared using the on-treatment observation period. In terms of adverse events, as a minimum, serious adverse events will be tabulated separately also using the in-trial observation period.

All events in the in-trial observation period will be listed with information about whether it appeared in the on-treatment observation period or not.

Number of treatment emergent Adverse Events (AEs)

AEs will be coded using the Medical Dictionary for Regulatory Activities (MedDRA). AEs will be presented based on system organ class and preferred terms.

A Treatment Emergent Adverse Event (TEAE) is defined as an event that has an onset date on or after the first day of exposure to randomised treatment, and no later than seven days after the last day of randomised treatment.

TEAEs are summarised descriptively, whereas AEs not defined as treatment emergent are presented in listings, including AEs reported in the 30-day follow-up period. The summaries of TEAEs are made displaying the number of Subjects with at least one event, the percentage of Subjects with at least one event, the number of events and the event rate per 100 patient years of exposure. These summaries are done by seriousness, severity, relation to insulin treatment, relation to technical complaint, premature treatment discontinuation due to AEs, AEs leading to withdrawal from trial and outcome.

Furthermore, summary tables based on system organ class and preferred terms are made for:

- All TEAEs
- Serious TEAEs
- Possibly or probably related TEAEs
- Severe TEAEs
- TEAEs with preferred term that are experienced by at least 5% of the Subjects in any treatment arm or by at least 5% of all Subjects

For AEs where additional information is recorded, this will be listed.

AEs occurring during the run-in period are considered non-treatment emergent and will be summarised separately.

Number of treatment emergent infusion site reactions

Infusion site reactions occurring during the trial will be summarised using the on-treatment observation periods, and listed.

Classification of Hypoglycaemia

Treatment emergent: hypoglycaemic episodes will be defined as treatment emergent if the onset of the episode occurs on or after the first day of IMP administration after randomisation and no later than one day after the last day on IMP.

Nocturnal hypoglycaemic episodes: are episodes occurring between 00:01 and 05.59 both inclusive.

[figure not shown]
Hypoglycaemic episodes are classified according to the Novo Nordisk classification of hypoglycaemia (see [Figure 2-1](#)) and the American Diabetes Association (ADA) classification of hypoglycaemia (see [Figure 2-2](#)).

Novo Nordisk classification of hypoglycaemia

In normal physiology, symptoms of hypoglycaemia occur below a PG level of 3.1 mmol/L [56 mg/dL].³ Therefore, Novo Nordisk has included hypoglycaemia with PG levels below this cut-off point in the definition of blood glucose (BG) confirmed hypoglycaemia.

Novo Nordisk uses the following classification (see [Figure 2-1](#)) in addition to the ADA classification:

- Severe hypoglycaemia according to the ADA classification⁴
- Severe or BG confirmed hypoglycaemia: An episode that is severe according to the ADA classification⁴ or BG confirmed by a PG value <3.1 mmol/L [56 mg/dL] **with or without** symptoms consistent with hypoglycaemia

[figure not shown]

Note: Glucose measurements are performed with capillary blood calibrated to plasma equivalent glucose values

Figure 2-1 Novo Nordisk classification of hypoglycaemia

ADA classification⁴ of hypoglycaemia

- Severe hypoglycaemia: An episode requiring assistance of another person to actively administer carbohydrate, glucagon, or take other corrective actions. PG concentrations may not be available during an event, but neurological recovery following the return of PG to normal is considered sufficient evidence that the event was induced by a low PG concentration
- Asymptomatic hypoglycaemia: An episode not accompanied by typical symptoms of hypoglycaemia, but with a measured PG concentration ≤ 3.9 mmol/L [70 mg/dL]
- Documented symptomatic hypoglycaemia: An episode during which typical symptoms of hypoglycaemia are accompanied by a measured PG concentration ≤ 3.9 mmol/L [70 mg/dL]
- Pseudo-hypoglycaemia: An episode during which the person with diabetes reports any of the typical symptoms of hypoglycaemia with a measured PG concentration > 3.9 mmol/L [70 mg/dL] but approaching that level
- Probable symptomatic hypoglycaemia: An episode during which symptoms of hypoglycaemia are not accompanied by a PG determination but that was presumably caused by a PG concentration ≤ 3.9 mmol/L [70 mg/dL]

Note: Glucose measurements are performed with capillary blood calibrated to plasma equivalent glucose values

Figure 2–2 ADA classification of hypoglycaemia

Data on-treatment emergent hypoglycaemic episodes are presented in terms of the number of Subjects with at least one event (N), the percentage of Subjects with at least one event (%), the number of events (E) and the event rate per 100 years of exposure (R). Separate summaries are made by severity considering all episodes, nocturnal and daytime episodes using Novo Nordisk and ADA classified episodes. All episodes will also be summarised by category, including summaries in relation to time since start of meal, as occurring within the following time intervals:

- During first 1, 2 and 4 hours after the start of the meal
- Between 1 (exclusive) to 2 hours (inclusive) after start of meal
- Between 2 (exclusive) to 3 hours (inclusive) after start of meal
- Between 3 (exclusive) to 4 hours (inclusive) after start of meal
- Between 2 (exclusive) to 4 hours (inclusive) after start of meal

Non-treatment emergent hypoglycaemic episodes will be listed.

The number of treatment emergent severe or BG confirmed hypoglycaemic episodes (all, daytime, nocturnal, 1 hour, 2 hour, 4 hour, 1 (exclusive) to 2 hours (inclusive), 2 (exclusive) to 3 hours (inclusive), 3 (exclusive) to 4 hours (inclusive), and 2 (exclusive) to 4 hours (inclusive) after start of the meal) will be analysed based on the FAS using a negative binomial regression model with a log-link function and the logarithm of the time period in which a hypoglycaemic episode is considered

treatment emergent as offset. The model will include treatment, strata (two levels based on use of own CGM or not), previous insulin use (three levels: NovoRapid[®], Apidra[®], Humalog[®]), and region as factors. To the extent where data allow, separate analyses will be performed for all severe episodes.

Number of unexplained episodes of hyperglycaemia (confirmed by SMPG)

The number of unexplained episodes of hyperglycaemia will be summarised in a frequency table. Unexplained hyperglycaemia is defined as a confirmed PG value ≥ 16.7 mmol/L (300 mg/dL) and is unexplained (i.e. no apparent medical, dietary, insulin dosage or pump failure reason). The percentage of Subjects with unexplained hyperglycaemia will be presented.

Unexplained hyperglycaemic episodes will be defined as treatment emergent if the onset of the episode occurs on or after the first day of IMP administration after randomisation and no later than one day after the last day on IMP.

Physical examination

The physical examination parameters (head, ears, eyes, nose, throat, neck, respiratory system, cardiovascular system, gastrointestinal system incl. mouth, musculoskeletal system, central and peripheral nervous system, skin), and their change from baseline, will be summarised descriptively. All findings will be listed.

Electrocardiogram

Electrocardiogram (ECG) findings will be summarised descriptively including summaries of the change from screening. Change from screening will be summarised as normal/abnormal not clinically significant/abnormal clinically significant categorisation in shift tables.

Vital signs (blood pressure, pulse)

Vital signs include diastolic blood pressure, systolic blood pressure and pulse. The measurements will be summarised descriptively using both the actual values as mean change.

Fundus photography/fundoscopy

Fundus photography/fundoscopy findings and the change from screening will be summarised descriptively.

Clinical laboratory assessments

Change from baseline 16 weeks after randomisation in central laboratory assessments:

- Haematology (haemoglobin, haematocrit, erythrocytes, thrombocytes, and leucocytes)
- Biochemistry (total protein, creatinine, alanine aminotransferase (ALT), aspartate aminotransferase (AST), alkaline phosphatase (AP), sodium, potassium, albumin, and total bilirubin)
- Urinalysis (albumin/creatinine ratio, erythrocytes, protein, and ketones)

Individual laboratory values will be compared to their relevant reference range (when existing) and flagged as being below or above the range. The measurements and their change from baseline will be summarised descriptively. Change from baseline will be summarised descriptively using both the actual values and the low/normal/high categorisation in shift tables.

Change from baseline in body weight and body mass index (BMI) 16 weeks after randomisation

The measurements will be summarised descriptively using the actual values as mean change.

Change from baseline in body weight will be analysed using a statistical model similar to 1), except with the corresponding baseline measurement as covariate. The analysis will be based on the safety analysis set and the on-treatment observation period.

Number of change-of-infusion-sets per week during 16 weeks after randomisation

For each Subject this is calculated as the total number of infusion sets used divided by the actual duration of the randomised treatment period in days, multiplied by seven. It will be summarised for each treatment using descriptive statistics.

Number of Subjects with at least one non-routine change categorised by reasons for change

The percentage of Subjects with at least one non-routine change will be presented, categorised by reasons for change, in a frequency table by treatment.

3 Changes to the statistical analyses planned in the protocol

General considerations

It has been clarified how data collected at visit 22A and 22B are handled.

Statistical analysis

It has been clarified that type 1 error will only be controlled for the primary estimand.

In the sensitivity analysis 2) for change from baseline in HbA_{1c} it has been clarified that baseline HbA_{1c} is still included in the analysis as a covariate.

In the statistical analysis in the protocol it is not clear if missing values or values for subjects discontinuing treatment/withdraw from trial should be imputed. Some of the following changes have been implemented to account for this issue.

In the sensitivity analysis for change from baseline in HbA_{1c} it has been changed from subjects withdrawing from trial to subjects with an imputed value at week 16 to be aligned with the primary analysis.

In the statistical sensitivity analysis 3b) for change from baseline in HbA_{1c} copy reference has been changed to conditional imputation, and for 3c) jump to reference has been changed to unconditional imputation to clarified the method used.

It has been clarified that the statistical analysis 4) will be repeated as for the confirmatory secondary endpoints.

For change from baseline in 1-hour PPG increment (meal test) it has been clarified how the endpoint is derived, which is aligned with the other endpoints derived from the meal test. To align with the primary analysis it has been changed so values at week 16 are imputed for subjects with missing values instead of imputing values for subjects withdrawn from trial, and the imputations are based on subjects in the NovoRapid[®] arm with non-missing values instead of completers in the NovoRapid[®] arm.

For the statistical analysis of change from baseline of time spent in low IG (≤ 3.9 mmol/L) it has been clarified that the corresponding baseline value will be included as covariate.

In the statistical analysis for subjects reaching HbA_{1c} or PPG (SMPG) targets it has been clarified that subjects without an HbA_{1c} measurement or 1-hour mean PPG measurement at week 16 will be handled as non-responders in the on-treatment observation period analysis.

Change from baseline has been removed for fluctuation in the 7-7-9-point SMPG profile as it is analysed logarithmically transformed and change from baseline values could be negative.

CGM endpoints

Percentage of time spent with IG ≤ 3.9 mmol/L [70 mg/dL] has been added to align with the thresholds for IG for the endpoints incidence of episodes.

The percentage of time spent with IG > 13.9 mmol/L [250 mg/dL] and incidence of episodes with IG > 13.9 mmol/L [250 mg/dL] has been added to further evaluate the effect and safety of fast-acting insulin aspart.

It has been clarified the variation in the IG profile will be presented by the fluctuation.

The change from baseline in $\Delta\text{AUC}_{\text{IG},0-15\text{min}}$, $\Delta\text{AUC}_{\text{IG},0-30\text{min}}$, $\Delta\text{AUC}_{\text{IG},0-1\text{h}}$, $\Delta\text{AUC}_{\text{IG},0-2\text{h}}$ and $\Delta\text{AUC}_{\text{IG},0-4\text{h}}$ are added to further evaluate the effect and safety of fast-acting insulin aspart.

It has been clarified that the endpoints related to CGM and meal test derived as AUCs will be weighted by the duration.

Adverse events

For adverse events summaries by relation to device has been change to relation to technical complaint to align with what is reported on the case report forms. Summaries for AEs leading to withdrawal from trial have been added to further investigate the safety of fast -acting insulin aspart.

Hypoglycaemic episodes

The endpoints treatment emergent hypoglycaemic episodes occurring within 1 (exclusive) to 2 hours (inclusive), 2 (exclusive) to 3 hours (inclusive), 3 (exclusive) to 4 hours (inclusive) after start of the meal has been added to further investigate the safety of fast-acting insulin aspart.

It has been clarified that separate statistical analysis will only be for all severe hypoglycaemic episodes as the number is expected to be very low.

Unexplained hyperglycaemic episodes

The treatment emergent definition for unexplained hyperglycaemic episodes has been clarified.

Assessments not collected at baseline

ECG and fundus photography/fundoscopy is not collected at baseline, hence change from screening will be summarised for these endpoints instead.

4 References

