8.1.4 Randomisation

Randomisation (Visit 6) should occur after the four-week run-in period has been completed.

The Subject must attend randomisation (Visit 6) fasting. For definition of fasting, please see section 8.1.7.

If the Subject meets the randomisation criterion at Visit 6, the Subject will be randomised into one of the two treatment arms by using IV/WRS; please see section 10. The Subject will undergo a meal test (please see section 8.3.7). When the meal test is completed the Subject will be instructed to discontinue their current insulin and start treatment with the trial product according to randomisation. A new infusion set and reservoir containing trial product must be inserted while the Subject is still at site. Stop date of the current insulin treatment and start date of the randomised trial product must be recorded in the eCRF.

Subjects will keep the same Subject number as allocated at screening.

For randomisation (Visit 6) procedures, please see flowchart in section 2.

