8.3.2.3 Change of infusion set and reservoir

Infusion sets (Medtronic Quick-Set[®], Medtronic Mio[®], Medtronic Silhouette[®] or Medtronic SureT[®] (Easy-set®)) and reservoirs (1.8/3.0 mL) will be provided by Novo Nordisk. Infusion sets and reservoirs will be dispensed at site visits indicated in the flowchart in section 2. The type of infusion set and size of reservoir should be recorded in the eCRF at each dispensing visit.

The Subjects should be instructed to routinely change infusion set in intervals not exceeding 3 days (2 days for SureT[®] (Easy-set[®])). Infusion set and reservoir should be changed at the same time. The trial products should preferably be administered in the abdominal wall. The Investigator should ensure that the Subject is instructed in the following:

Protocol
Trial ID: NN1218-3854

CONFIDENTIAL

Date: 04 February 2016 | Novo Nordisk
Version: 4.0

• The infusion region chosen should remain unchanged throughout the trial

- The infusion site should be rotated within the same region
- The infusion set should preferably be inserted in the same way

The Subject should change infusion set and reservoir at the site under supervision by the Investigator at randomisation (Visit 6) and at end of treatment (Visit 22) due to the change from pre-trial insulin to trial product. The Investigator should evaluate the skin for any local skin irritation or skin infection at every visit at the clinic. Any abnormal clinically significant findings should be recorded as an infusion site reaction, as detailed in section 8.3.3.3.

The Subject should be instructed to record all infusion set change in their diary. Investigator should ensure that instructions for change are being followed by reviewing the CareLink Report. The review must be documented by signing the CareLink Report. Infusion set changes can be considered as a 'routine change' or 'non-routine change'.

Routine change

A routine change of the infusion set and reservoir is defined as a regular change performed in no more than 3-days intervals (2 days for SureT®(Easy-set®)). Infusion set change at site in the morning the day before randomisation (Visit 6) and end of treatment (Visit 22) are considered a routine change. All infusion set changes due to Subject's decision and not due to any problem with the pump, the infusion set or glucose values (e.g. inconvenient location of infusion set) must be considered a routine change.

Non-routine change

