180		X	
240		X	
End of meal test			X (Subject's safety)

^{*}All blood samples must be sent to the central laboratory for analysis

Laboratory results from meal test data will be loaded directly into the trial database by the central laboratory. The meal test results will not be provided to the Investigator until after EoT (Visit 24).

The Subject should wait in the clinic to have the blood samples drawn after 30 minutes, 1, 2, 3 and 4 hours from the start of the standardised meal, as detailed in Table 8–2. During the meal test the Subject should be resting in a chair. No smoking or intake of meals and liquids will be allowed during the meal test, except for water, which is allowed two hours after intake of the standardised meal.

If SMPG values \leq 3.9 mmol/L [70 mg/dL] are measured then the hypoglycaemia should be treated according to local practice and the meal test should continue according to the Investigator's discretion. The hypoglycaemic episode must be reported. Please see section 8.3.3.1.

The following must be recorded in the eCRF in relation to the meal test:

- Fasting status
- Time and value of SMPG measurement confirming that the Subject's glucose is within the target of 4.0-8.8 mmol/L (71-160 mg/dL)
- Body weight
- Start and end-time of standardised meal
- Volume and carbohydrate content of standardised meal consumed
- Confirmation that the Subject consumed the required volume of the standardised meal
- Batch number of standardised meal consumed
- Time of blood samples
- Hypoglycaemic episode number, if relevant
 - Time of intervention and amount of glucose rescue treatment

Protocol		Date:	04 February 2016	Novo Nordisk
Trial ID: NN1218-3854	CONFIDENTIAL	Version:	4.0	
LITTLE 111111 1110 0100	CONFIDENTIAL	G	T: 1	

Status:

Page:

Final

69 of 149

After the meal test, the Investigator should make sure that the Subject is safe to leave the site

When the meal test is finished, the Novo Nordisk provided CGM device should be removed and data uploaded to the computer by the Investigator, please see section 8.5.1.5.

When the meal test at randomisation (Visit 6) is completed, the Subject will be instructed to discontinue their current insulin and start treatment with randomised trial product. When the meal test at the end of treatment (Visit 22) is completed, the Subject will be switched to a marketed insulin product according to Investigator's discretion as detailed in section 5.5.

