Treatment emergent: hypoglycaemic episodes will be defined as treatment emergent if the onset of the episode occurs on or after the first day of IMP administration after randomisation and no later than one day after the last day on IMP.

Nocturnal hypoglycaemic episodes: are episodes occurring between 00:01 and 05.59 both inclusive.

Hypoglycaemic episodes are classified according to the Novo Nordisk classification of hypoglycaemia (see Figure 17–1) and the American Diabetes Association (ADA) classification of hypoglycaemia (see Figure 17–2).

04 February 2016 | Novo Nordisk Protocol Date: Trial ID: NN1218-3854 Version: 4.0 CONFIDENTIAL Final

Status:

125 of 149

Page:

[figure not shown]
UTN: U1111-1118-2480 EudraCT no.: 2010-024054-11

Novo Nordisk classification of hypoglycaemia

In normal physiology, symptoms of hypoglycaemia occur below a PG level of 3.1 mmol/L [56] mg/dL]³⁶. Therefore, Novo Nordisk has included hypoglycaemia with PG levels below this cut-off point in the definition of BG confirmed hypoglycaemia.

Novo Nordisk uses the following classification (see Figure 17–1) in addition to the ADA classification:

- Severe hypoglycaemia according to the ADA classification²⁹
- Severe or BG confirmed hypoglycaemia: An episode that is severe according to the ADA classification²⁹ or BG confirmed by a PG value <3.1 mmol/L [56 mg/dL] with or without symptoms consistent with hypoglycaemia

Note: Glucose measurements are performed with capillary blood calibrated to plasma equivalent glucose values

Figure 17-1 Novo Nordisk classification of hypoglycaemia

ADA classification²⁹ of hypoglycaemia

[figure not shown]
- Severe hypoglycaemia: An episode requiring assistance of another person to actively administer carbohydrate, glucagon, or take other corrective actions. PG concentrations may not be available during an event, but neurological recovery following the return of PG to normal is considered sufficient evidence that the event was induced by a low PG concentration
- Asymptomatic hypoglycaemia: An episode not accompanied by typical symptoms of hypoglycaemia, but with a measured PG concentration ≤3.9 mmol/L [70 mg/dL]

Protocol		Date:	04 February 2016	Novo Nordisk
Trial ID: NN1218-3854	CONFIDENTIAL	Version:	4.0	
UTN: U1111-1118-2480	CONFIDENTIAL	Status:	Final	

Page:

126 of 149

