1.2 Scope of the statistical analysis plan

This statistical analysis plan (SAP) is based on the statistical considerations of NN1218-3854 as planned in the trial protocol *Efficacy and Safety of Continuous Subcutaneous Insulin Infusion of Faster-acting Insulin Aspart compared to NovoRapid[®] in Adults with Type 1 Diabetes*, version 4.0 (dated 04 February 2016). It contains a more detailed description for deriving and calculation of endpoints. Furthermore, it details changes to the statistical considerations presented in the protocol.

The changes to the statistical considerations proposed in this SAP and the reasons for the changes will be reported in the clinical trial report (CTR).

2 Statistical considerations

General considerations

In general, for endpoints evaluated as a change from baseline and/or where a baseline adjustment is made, baseline is defined as information collected at randomisation (Visit 6). In case a measurement is not available at randomisation, the most recent measurement prior to randomisation will be used as baseline.

Two observation periods are defined, “in-trial” and “on-treatment”, and it will be specified which period each analysis will use.

- **In-trial:** the observation period from date of randomisation and until last trial -related Subject-site contact. The in-trial observation period includes data collected after discontinuation of randomised treatment.
- **On-treatment:** the observation period from date of first dose of randomised NovoRapid[®]/fast-acting insulin aspart and no later than 7 days after the day of last dose of randomised NovoRapid[®]/fast-acting insulin aspart. The on-treatment observation period includes data collected up to and including 7 days after discontinuation of randomised treatment.

All efficacy endpoints will be summarised and analysed using the full analysis set (FAS), unless otherwise stated. Safety endpoints will be summarised using the safety analysis set and analysed using the FAS.

Presentation of results from a statistical analysis will include the estimated mean treatment effects (LSMeans) for change from baseline, if applicable. Estimated mean treatment differences (or ratios) will be presented together with two-sided 95% confidence interval (CI) for all endpoints analysed statistically.

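### Treatment-emergent hypoglycaemia starts by calendar day, so an episode in the Visit 6 meal test, before any trial product, meets the definition and conflicts with two general rules in the SAP

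*SAP*

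**What the plan says.** **Start of the window.** SAP section 2.4.2.2 counts an episode as treatment emergent "if the onset of the episode occurs on or after the first day of IMP administration after randomisation", ending one day after the last day on trial product. Protocol section 17.4.2.2 uses the same rule: "the onset of the episode occurs on or after the first day of IMP administration after randomisation". The on-treatment period, used for all safety comparisons, is also set by date. SAP section 2 (General considerations) defines it as "the observation period from date of first dose of randomised" trial insulin.

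**What happens on that day.** Under Protocol section 8.1.2 subjects stay on their current insulin until Visit 6. Section 8.1.4 then says: "When the meal test is completed the Subject will be instructed to discontinue their current insulin and start treatment with the trial product". It continues: "A new infusion set and reservoir containing trial product must be inserted while the Subject is still at site". For a low glucose value during the test, section 8.3.7 says: "The hypoglycaemic episode must be reported".

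**What is analysed.** SAP section 2.4.2.2 fits a negative binomial model to severe or BG confirmed episodes, overall and in windows up to 4 hours after the start of a meal. The offset is the log of the treatment-emergent period.

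**Rules that point the other way.** SAP section 2 limits data from before randomisation to descriptive summaries. SAP section 2.4.2.2 treats run-in adverse events as non-treatment emergent.

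**Infusion sites.** These reactions are summarised over the same date-based on-treatment period. Protocol section 8.3.2.3 adds a check: "The Investigator should evaluate the skin for any local skin irritation or skin infection at every visit at the clinic".

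**The concern.** A treatment-emergent count should hold events that could follow from the randomised product. Visit 6 is the first day of trial product for every subject, and a provocation test on the previous insulin is completed earlier that day. The written rule cannot tell the two parts of the day apart. Any in-test episode below the threshold is attributed to a randomised arm although neither product has been given.

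The post-meal windows are where this could matter most. Protocol section 3.1.2 reports that, in an earlier injection trial, the rate in the first hour after a meal was significantly higher with faster aspart, within a small fraction of all episodes. In a sparse window a few unrelated counts weigh more, and equal additions to both arms pull a ratio towards 1.

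The second issue is reproducibility. The specific definition and the general rules give different answers for the same episode, so two programmers could both follow the plan and report different counts.

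**Working it through.** The plan states no figure on this point, so there is none to reproduce. The check has two parts.

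**1. Do the rules classify an in-test episode consistently?**

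- *Hypoglycaemia definition (SAP 2.4.2.2, Protocol 17.4.2.2):* onset falls on the first day of trial product, so the episode is treatment emergent.
- *Pre-randomisation rule (SAP section 2):* the answer depends on the order of events. Protocol 8.3.7 puts randomisation after the meal test, which makes the episode descriptive only. Protocol 8.1.4 describes randomisation first and the test second, in which case the rule does not reach the episode.
- *Run-in rule (SAP 2.4.2.2):* Protocol 12.1.1 regards non-serious hypoglycaemia as an adverse event, and 8.1.3 describes run-in as Visit 2 to Visit 6. Whether the pre-dose part of Visit 6 belongs to run-in is not stated.
- *Meal-test exclusion (SAP 2.4.2.1):* this removes meal-test readings from CGM endpoints only. Nothing similar is written for hypoglycaemic episodes.

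Under Protocol 8.3.7, hypoglycaemia from midnight onwards postpones the test. The pre-dose episodes at issue are therefore mainly those arising in the test itself.

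**2. How large is the effect?**

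Time at risk: days 0 to 112 plus one day is 114 days. The test covers 4 hours, so its share is (4/24)/114 = 0.15%. Over 450 subjects that is 450 × 4/24 = 75 subject-days.

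Let λ be the comparator's genuine events per subject in a window over 16 weeks, RR the true rate ratio, and p the in-test events per subject, equal in both arms. The offset is the same in both arms, so

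observed ratio = (λ × RR + p) / (λ + p).

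The documents give none of λ, RR or p; all three are assumptions. With p from 0.01 to 0.05, 450 subjects would give 450 × 0.01 = 4.5 to 450 × 0.05 = 22.5 in-test episodes. For a true ratio of 1.5:

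| λ | p = 0.003 | p = 0.01 | p = 0.03 | p = 0.05 |
|---|---|---|---|---|
| 0.5 | 1.497 | 1.490 | 1.472 | 1.455 |
| 0.25 | 1.494 | 1.481 | 1.446 | 1.417 |
| 0.1 | 1.485 | 1.455 | 1.385 | 1.333 |
| 12 (all episodes) | 1.4999 | 1.4996 | 1.4988 | 1.4979 |

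Two cells written out:

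- λ = 0.5, p = 0.01: (0.75 + 0.01)/0.51 = 1.490
- λ = 0.1, p = 0.05: (0.15 + 0.05)/0.15 = 1.333

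In the second, in-test episodes are 0.05/0.15 = one third of the comparator's count, which is why it is extreme. With RR = 1 the formula gives (λ + p)/(λ + p) = 1, so no difference is created.

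The comparator's rate is overstated by p/λ: 0.01/0.5 = 2% in the first case, 0.05/0.1 = 50% in the extreme one, and at most 0.05/12 = 0.4% for all episodes.

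**The case against.** The strongest reply is that the plan, read as a whole, already excludes these episodes: randomisation follows the test, pre-randomisation data are descriptive, and run-in events are not treatment emergent. That is a reasonable reading and probably the intended one. It does not settle the matter. The specific definition says otherwise, the protocol contradicts itself on the order of events, and the boundary of run-in at Visit 6 is not drawn.

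A second reply is that few episodes will qualify. The model takes only severe episodes or plasma glucose below 3.1 mmol/L. Subjects should start the test between 4.0 and 8.8 mmol/L and then take 78 g of carbohydrate. In-test meter readings are taken only as safety requires. This stands, and it makes the upper end of the assumed range for p less plausible. The ADA summaries, at 3.9 mmol/L or below, would take in more.

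A reader might infer that every in-test episode lands in a post-meal window. The documents do not establish that. The hypoglycaemia form (Protocol 8.3.3.1) asks for the time of the last main meal, and nothing says whether the liquid test meal is one. If a site enters the previous evening's meal, the episode falls outside all the windows. Even if the test meal counts, only the 0–4 hour window is sure to hold all in-test episodes. It also has the most genuine events, so dilution there is least.

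A reader might also infer that the rule favours one product or could hide the first-hour signal. Both arms are on pre-trial insulin during the test, so equal numbers are expected and the effect is dilution. The documents contain no in-test rate that would make it material, and these analyses lie outside the confirmatory testing hierarchy.

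**Conclusion.** The point holds as a fault in the counting rule. As written, a hypoglycaemic episode in the Visit 6 meal test meets the treatment-emergent definition before any trial product is given, and this is not reconciled with the two general rules or with the protocol's two orders of events.

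The numerical consequence is modest. For all episodes it is negligible. For post-meal windows it arises only if the test meal counts as the meal, and an assumed ratio of 1.5 then usually stays close to its true value (1.49 at λ = 0.5, p = 0.01). A fall to about 1.33 needs both a very sparse window and frequent in-test episodes within it. These figures assume equal in-test rates in the two arms.

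For infusion site reactions the same issue is conditional: a reaction at the old site counts only if its onset is dated to Visit 6. They are summarised and listed, not modelled. General adverse events share the date-based start, but the documents show no clock time for their onset, so a time rule is not supported for them. The reason to act is that safety events are misattributed and the correction is nearly free. A large expected shift in any estimate is not the reason.

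**What to change.** In SAP section 2.4.2.2:

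- Start the hypoglycaemia treatment-emergent window, and the model offset, at the recorded date and time when the first infusion set with trial product is inserted at Visit 6.
- Classify Visit 6 episodes with earlier onset, including those linked to the meal test, as non-treatment emergent and list them with the run-in episodes.
- State whether meal-test episodes count in the post-meal windows. The Visit 22 test raises the same question, although there the subject is on trial product.
- Apply the same time-based start to infusion site reactions where the set-change time is recorded.

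Protocol sections 8.1.4 and 8.3.7 should be reconciled on the order of randomisation and meal test. The time-based rule works under either order.

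The cost is a few sentences and a date-time comparison in programming. The data are already collected: episode onset date and time (Protocol 8.3.3.1), date and time of every set change (8.3.2.3), the episode number and meal times for the meal test (8.3.7), and the last set change before an infusion site reaction (8.3.3.3). The eCRF start entry for trial product is a date only (8.1.4), so the set-change record should be named as the source.
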